The purpose of the treatment period is to establish the impact of ENT-01 on CSBM rates. The purpose of the placebo period is to determine the duration of the treatment effect once study medication is discontinued. At this visit, all subjects will be given placebo and will continue taking the same number of tablets as they were taking at the maximum “fixed” dose period. The subject will not be made aware that the study medication provided is a placebo.

During this visit, the following assessments and procedures will be performed:

- Brief Physical Exam
- Weight
- Orthostatic Vital Signs – 3 sets: See screening description
- 12-lead ECG
- Labs and urinalysis as defined in [APPENDIX 1](#).
- Pregnancy Testing - For women of child-bearing potential only.
- IP/Placebo Collection and Accountability
- Single-blind Placebo Dispensation
- For subjects participating in the L-Dopa sub-study, subjects will be instructed to come to clinic as early as possible and on an empty stomach. They will first take their study medication (ENT-01 or placebo) in clinic. Thirty minutes after the ENT-01/placebo dose, subjects will take their morning dose of levodopa.
- Levodopa PK Draws - Blood samples will be obtained before the -L-Dopa dose and at 20,

40 and 60 minutes after the dose

- IP/Placebo Collection and Accountability
- Dispense Rescue Medication, as needed. Subjects continue appropriate use of rescue medication, ensuring adequate bowel movements every 3 days.
- Stool Diary Review
- AE Review
- Prior and Concomitant Meds
- MDS-UPDRS - The MDS-UPDRS should be administered while the subject is in an ON state, approximately one hour after taking levodopa (if applicable), or whenever “ON” occurs.
- Questionnaires:
 - C-SSRS
 - BDI-II
 - MMSE
 - PAC-SYM
 - PAC-QOL
 - SAPS-PD and hallucination questionnaire (if applicable)
- Collect Stool Sample (if applicable)

4.5 Visit 5: End of placebo period/ beginning of Wash-Out (Study Day 39) (+/- 8 days)

The purpose of the Wash-out period is to determine the duration of treatment effect. Subjects will be taken off placebo (study medication). They will continue to keep daily stool diaries for the duration of this period. During the first 3 weeks, subjects will continue to use rescue medication as needed. The following day, i.e., day 22 of the Wash-Out Period, subjects will be instructed to restart all their original medications, including oral laxatives.

During this visit, the following assessments and procedures will be performed:

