5.7 Concomitant and Prohibited Medication

- Preventive laxatives will be discontinued during the screening period. This will include all prescription laxatives, over the counter laxatives and dietary supplements. Throughout the study, subjects will be allowed to take constipation rescue medication on demand, and only if they have not had a bowel movement in three consecutive days. Rescue medications will be recorded in the electronic daily diary every time a laxative is used. Bowel movement produced within 24 hours of rescue medication or accidental self-prescribed laxative use will not be counted as either spontaneous bowel movement or complete spontaneous bowel movement.
- Proton pump inhibitors and antacids will be discontinued at the end of the screening period and reinstated during the wash-out period.
- Barbiturates, and opiates will be discontinued at the end of the screening period and 2-3 days before dosing and reinstated during the wash-out period. All medications shall be reviewed and dis/approved by the investigator on a case-by-case basis.
- Selective serotonin reuptake inhibitor (SSRI), SNRI, tricyclic antidepressant, anti-cholinergic, anti-histaminergic and anti-psychotic agents are permissible at stable doses.
- Dopamine agonists and amantadine will be allowed if on a stable dose for at least 2 weeks preceding the study.
- Deep brain stimulation is allowed if present for more than 6 months and at stable stimulation parameters.

Subgroup Analyses

[figure not shown]
Subjects will be analyzed overall by their randomized treatment assignment (i.e., active versus placebo). Subgroup analyses will also be performed by a subject's baseline CSBM rate (i.e., 0-0.9, or 1.0-3.0). The primary efficacy endpoint and key secondary, exploratory and safety endpoints will be summarized by these subgroups. Additional subgroup analyses may be defined in the statistical analysis plan (SAP).

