2.5. Study Periods

The study consists of the following periods:

1. **Screening Period:** This period lasts from Visit 1 to the day before Visit 2 (Day of randomization)
2. **Treatment Period:** This period lasts from Visit 2 (day of randomization) to the day before Visit 4 (start of single blind placebo period) and is divided into two sub-periods
 - 2.1. **Dose Escalation Period:** This period starts at Visit 2 and ends when the subject is on a Fixed Dose of study medication.
 - 2.2. **Fixed Dose Period:** This period starts when the subject is on a Fixed Dose of study medication and lasts until Visit 4. The fixed dose period is only defined if the subject was in the treatment period for at least seven days after the date of randomization. In the event that a subject is on the same dose until the start of the single blind placebo period or until withdrawal from treatment after being in the treatment period for at least seven days after randomization, then the fixed dose period will be the entire treatment period and the dose escalation period will not be defined. If the subject was not on their fixed dose for at least seven days, then the fixed dose period will extend to the subject's last seven days of treatment (including fixed dose) in order to derived rate variables during the fixed dose period, as described in Section 4.7. Missing diary entries in the middle of treatments of the same dose are not considered when determining the start of the fixed dose period.
3. **Single Blind Placebo Withdrawal Period:** This period starts at Visit 4 and ends at Visit 5. Weekly rate derivations during the single blind placebo withdrawal period will not include assessments on the Visit 4 date.
4. **Wash Out Period:** This period starts at Visit 5 and ends at Visit 6.

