A patient’s CSBM weekly rate over a particular period will be derived using the following algorithm:

Weekly CSBM Rate = $7 \times \{\# \text{ of CSBMs in the period}\} / \{\# \text{ of days in the period}\}$

The weekly SBM rate calculations use the same algorithm.

If a patient is missing BM information for a day, it will be assumed that the patient had 0 SBMs and 0 CSBMs for that period (with the exceptions in calculating Baseline CSBM and SBM rates noted in Section 2.6).

If a subject diary has “repeat” stool data (eg, a BM repeated with the same date/time of BM) only the latest duplicate observation relative to when the patient entered the data into the diary will be used.

For the calculation of the Baseline CSBM (SBM) weekly rate:

- If the patient has more than 14 days of diary data during the Screening Period, only the last 14 days with non-missing diary entries prior to the randomization visit will be used (i.e., the days which are more than 14 days prior to the randomization visit will be excluded)
- If a patient has 11- 14 days of diary data, all available diary days will be used.
- If a subject has more than two weeks of entries during the screening period, consecutive missing entries during the screening period will be excluded from baseline calculations, and the last fourteen days with entries during the screening period will be used to derive baseline weekly rates.

For analyses of the CSBM (SBM) in the Fixed dose period, if a patient has not been in the Fixed Dose period for at least seven days, then the number of days used for calculating the weekly CSBM (SBM) rate will be adjusted to seven days by using the last “n” days of the Dose Escalation period leading up to the fixed dose period to get to 7 days in the Fixed Dose period. This derivation will be used for all efficacy endpoints for the Fixed Dose Period (e.g., stool ease of passage and stool consistency).

For analyses of the CSBM (SBM) rate during the single-blind placebo and washout periods, all available data in those periods, excluding observations on the date of the single-blind placebo visit as described before, will be used in the derivations of weekly rates described at the beginning of this section.

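### The washout CSBM and SBM rates include days after the planned laxative restart on washout day 22

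*SAP*

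**What the plan says.** Protocol 4.5 gives the aim: "The purpose of the Wash-out period is to determine the duration of treatment effect". On the diary it says: "They will continue to keep daily stool diaries for the duration of this period". On treatment for constipation it says: "During the first 3 weeks, subjects will continue to use rescue medication as needed". It then changes the conditions: on "day 22 of the Wash-Out Period, subjects will be instructed to restart all their original medications, including oral laxatives".

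The SAP does not pick up that change. SAP 2.5 defines washout without any inner cut: "This period starts at Visit 5 and ends at Visit 6". SAP 4.6.1 sets the data to be used: "For analyses of the CSBM (SBM) rate during the single-blind placebo and washout periods, all available data in those periods", with only the single-blind visit date removed. SAP 4.6.5 then analyses change from baseline in these rates by ANCOVA between the arms, and repeats the analysis with the fixed-dose value as baseline.

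The one related rule is the 24-hour exclusion. Protocol 5.7 says: "Bowel movement produced within 24 hours of rescue medication or accidental self-prescribed laxative use will not be counted" as spontaneous or complete spontaneous. In SAP 4.6.1, the cohort 1 CSBM definitions and the SBM definition rely on a diary question about rescue medication. The cohort 2 CSBM definitions equate rescue medication with laxative use recorded in the diary.

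**The concern.** Protocol 4.1 takes baseline off laxatives on purpose. The washout rate is then partly an on-laxative rate, so the change from baseline mixes two conditions. The share of each depends on when a subject happened to attend Visits 5 and 6.

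At stake is the washout half of the exploratory question about loss of efficacy after treatment stops. If both arms resume their usual laxatives, a lasting difference between ENT-01 and placebo would tend to be diluted, and the level in each arm would no longer describe bowel function without treatment. Ease of passage, consistency and suppository/enema use in washout cover the same days and have the same difficulty.

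**Working it through.** The plan gives no figure on this point to reproduce, so the check is a count of days followed by an illustration.

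**Inputs**
- Restart: washout day 22, after 3 × 7 = 21 days with rescue medication only (Protocol 4.5).
- Visit 5: Day 39 ± 8. Visit 6: Day 69 ± 8 (Protocol 4.5, 4.6 and Table 1). The SAP's schedule of events has narrower windows, ± 2 and ± 3 days.
- The Visit 5 date belongs to the single-blind period (SAP 4.6), so washout length L = Visit 6 day − Visit 5 day.
- Nominal length in the protocol synopsis: 4 weeks, or 28 days.

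**Share of washout days after the restart:** s = max(0, L − 21) / L

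| Case | L | Days from day 22 on | s |
|---|---|---|---|
| Four weeks exactly | 28 | 7 | 25% |
| Nominal visit days | 69 − 39 = 30 | 9 | 30% |
| Protocol windows, shortest | 61 − 47 = 14 | 0 | 0% |
| Protocol windows, longest | 77 − 31 = 46 | 25 | 54% |
| SAP windows, shortest | 66 − 41 = 25 | 4 | 16% |
| SAP windows, longest | 72 − 37 = 35 | 14 | 40% |

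**Effect on the rate.** The SAP's weekly rate is 7 × movements / days in the period. It is therefore a day-weighted average: reported rate = (1 − s) × rate on days 1–21 + s × rate from day 22 on.

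The 24-hour rule leaves two limiting cases for the second term:
- *Regular laxatives treated as rescue.* Movements within 24 hours of a dose are removed but their days stay in the denominator. At the limit the second term is 0 and the rate is biased down.
- *Regular laxatives not treated as rescue.* Movements produced by the laxative count as spontaneous and the rate is biased up. This is most plausible for SBMs and for cohort 1, where only rescue medication is queried.

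**Illustration.** The documents give no washout rates. The day 1–21 rates below, and the 4 per week after restart in the second case, are assumptions.

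| Assumed day 1–21 rates (ENT-01, placebo) | L | Reported if all later movements are removed | Reported if 4/week is counted in both arms | Arm difference, days 1–21 → all days |
|---|---|---|---|---|
| 3.0, 1.5 | 28 | 2.25, 1.125 | 3.25, 2.125 | 1.50 → 1.125 |
| 3.0, 1.5 | 30 | 2.10, 1.05 | 3.30, 2.25 | 1.50 → 1.05 |
| 3.0, 1.5 | 46 | 1.37, 0.68 | 3.54, 2.86 | 1.50 → 0.68 |
| 2.5, 2.0 | 28 | 1.875, 1.50 | 2.875, 2.50 | 0.50 → 0.375 |
| 2.5, 2.0 | 30 | 1.75, 1.40 | 2.95, 2.60 | 0.50 → 0.35 |
| 2.5, 2.0 | 46 | 1.14, 0.91 | 3.32, 3.09 | 0.50 → 0.23 |

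For L = 30, placebo: 21/30 × 1.5 = 1.05, or 1.05 + 9/30 × 4 = 2.25. The level moves in opposite directions in the two cases. The arm difference shrinks by the factor (1 − s) in both, because both give the two arms the same rate after restart.

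**The case against.** The strongest reply is that the harm is limited and partly handled already.

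- **Other evidence on duration.** The objective covers the single-blind placebo period as well as washout. That period precedes the restart, has its own rate, and shares the purpose of measuring how long the effect lasts. The linear trend test in SAP 4.6.3 ends there. A reader might infer that the duration question cannot be answered at all; the documents do not support that. On nominal days, 21 of 30 washout days are also free of the planned restart.
- **Who restarts.** A reader might infer that every subject goes back on laxatives. The text says only that subjects are instructed to restart what they took before. The current inclusion criteria do not require prior laxative use, and a short washout may end before day 22.
- **What is counted.** It is tempting to say that each later movement is either laxative-driven and counted, or scored as nothing. Movements more than 24 hours after a laxative count as spontaneous under the trial's own definition. For cohort 2 CSBMs, the wording points towards excluding movements within 24 hours of a recorded laxative. Actual rates could lie between the two limiting cases.
- **The top of the range.** The 54% needs the earliest Visit 5 and the latest Visit 6 in one subject. It is a bound, not a typical value.

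All four points stand and limit the claim. None removes the problem. The 24-hour rule was written for rescue and accidental use, and an instructed restart is neither. Where the rule does apply, it deletes movements and keeps their days.

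**Conclusion.** The point holds for the washout part of an exploratory objective. As written, the SAP averages days before and after a planned restart of laxatives. The later days make up about 25% to 30% of a nominal washout, and 0% to 54% at the extremes of the protocol windows. The day counts follow from the documents. They assume that the restart happens when instructed and that the Visit 5 date is not a washout day. For cohort 1 they also assume the same instruction, since that cohort's protocol version is not among the documents.

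The direction of bias in each arm's rate is not determined, because the SAP does not say how regular laxatives count. Dilution of the arm difference is likely but not established: it rests on assumed rates and on the arms behaving alike after restart. The primary endpoint, the success criterion, the single-blind placebo period and the trend test are unaffected. This should be corrected, but it does not threaten the main conclusion of the trial.

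**What to change.** In SAP 4.6.1 and 4.6.5:

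1. Derive washout CSBM and SBM rates, ease of passage, consistency and suppository/enema use from a fixed window of washout days 1 to 21, or to Visit 6 if that comes first.
2. Summarise day 22 onward separately.
3. State, by cohort and for both CSBM and SBM, whether regular laxative use counts as rescue under the 24-hour rule.
4. Do not censor at an earlier laxative restart in the main derivation. Subjects whose constipation returns sooner are more likely to restart early, so dropping their later days could bias the rate upward. Such censoring belongs in a sensitivity analysis.

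The cost is one or two SAP sentences and about 7 to 9 days per subject removed from the washout rate. Those days cannot measure off-treatment effect and remain available in the separate summary. No visit, data collection or instruction to subjects changes.

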1 STUDY SYNOPSIS

Study Title	A Multicenter, Randomized, Double-Blind, Placebo-Controlled, Multiple Dose Study to Evaluate Safety, Tolerability and Efficacy of Orally Administered ENT-01 for the Treatment of Parkinson's Disease-Related Constipation (KARMET)
Protocol Number	ENT-01-030
Study Phase	2b
Methodology	
This first part of this study was conducted as a multicenter, randomized, double-blind, placebo-controlled study. A subject's total study duration was no more than 10 weeks and total active dosing days was a maximum of 25 days. Approximately 72 subjects were randomized 3:1 to treatment or placebo (double-blind), with approximately 54 subjects allocated to the treatment groups and approximately 18 to placebo.
 
In this amendment, up to an additional 80 subjects (approximately) will be randomized 1:1 to treatment or placebo (double-blind) with approximately 40 subjects allocated to each group.
 
Randomization will be stratified on baseline weekly CSBM rate. Subjects with a baseline weekly CSBM rate of 1-3.0 will start with 3 tablets daily (3 placebo tablets or equivalent to 75 mg of ENT-01 if randomized to active treatment), while subjects with a baseline weekly CSBM rate of 0 - 0.9 will start with 6 tablets daily (6 placebo tablets, or equivalent to 150 mg of ENT-01 if randomized to active treatment).
 
Dose will then be increased by 25 mg (or 1 placebo tablet) every three days, until an effective dose is reached, up to a maximum dose of 10 tablets (i.e., 250 mg of ENT-01 if randomized to active treatment) or maximum tolerated dose (MTD) is reached, whichever comes first.
 
After completing up to 25 days of dosing, all subjects will be given placebo for 2 weeks (single-blind) followed by 4 weeks of wash-out.
 
The study will be conducted on an out-patient basis. Each subject will have 6 visits to the clinic: Visit 1/Screening Visit; Visit 2/Randomization Visit; Visit 3/Follow up Visit (during the dosing period); Visit 4/Single-Blind Placebo Withdrawal Period Visit; Visit 5/Washout Period; and Visit 6/ End of Study Visit.

Study Duration	Each subject will participate in the study for approximately 10 weeks. The duration of the amended study, from first subject enrolled to last subject last visit, is anticipated to be 6 to 9 months.
Study Centers	This is a multicenter trial at up to 25 U.S. sites.

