- SAPS-PD (if SAPS-PD score is greater than 0 on Visit 1 and 2, subject will have SAPS-PD and hallucination questionnaire administered at each subsequent visit).
- PAC-SYM
- PAC-QOL
- Collect Stool Sample (if participating in stool sub-study)
- Dispense IP/placebo and instruct subjects to take their second dose of study drug the following morning. Subjects will be advised to stay at home for 4-6 hours in case they need to evacuate urgently.

4.3 **Visit 3: Study Day 11 (+/- 3 days)**

The purpose of this visit is to evaluate the incidence of adverse events and to review the subject's dosing experience by reviewing ePRO entries with the subject.

During this visit, the following assessments and procedures will be performed:

- Brief Physical Exam
- Weight
- Orthostatic Vital Signs
- 12-lead ECG
- Labs and urinalysis as defined in [APPENDIX 1](#).
- Pregnancy Testing - For women of child-bearing potential only.
- For subjects participating in the L-Dopa sub-study, subjects will be instructed to come to clinic as early as possible and on an empty stomach. They will first take their study medication (ENT-01 or placebo) in clinic. Thirty minutes after the ENT-01/placebo dose, subjects will take their morning dose of levodopa.
- Levodopa PK Draws - Blood samples will be obtained before the L-Dopa dose and at 20, 40 and 60 minutes after the dose.
- IP/Placebo Drug Accountability and Dispensation
- Dispense Rescue Medication, as needed. Subjects continue appropriate use of rescue medication, ensuring adequate bowel movements every 3 days.
- Stool Diary Review
- AE Review
- Prior and Concomitant Meds
- MDS-UPDRS - The MDS-UPDRS should be administered while the subject is in an ON state, approximately one hour after taking levodopa (if applicable), or whenever the “ON” state occurs.
- Questionnaires:
 - C-SSRS
 - BDI-II
 - MMSE

- PAC-SYM
- PAC-QOL
- SAPS-PD and hallucination questionnaire (if applicable)
- Dispense Stool Collection Kit - Subjects participating in this sub-study will be given a stool collection kit so they can bring a stool sample at Visit 4.

4.4 Visit 4: End of treatment period/ Beginning of Placebo Period (Study Day 26)(- 2 days)

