If the start date has the year, but day and month are missing, the event will be considered treatment-emergent if the year of the start date of the event is the same as, or later than, the year of the date of the first dose of study drug.

Visit Windows

No visit windows will be applied.

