4.6. Efficacy Analyses

Efficacy analyses to evaluate the treatment effect will be conducted using the Fixed Dose population as the primary population. The analyses will also be performed using the mITT and Efficacy Evaluable populations. Summary statistics will also be presented.

The comparison of active versus placebo treatment will be tested at the two-sided 0.05 significance level.

The date of randomization will not be included for either baseline or post-baseline weekly efficacy endpoints (i.e., rates or mean values). Similarly, the date of the single-blind period visit will also not be used in derivation of weekly efficacy endpoints (rates or mean values). Also, the visit 5 Date (ie, the date the patient begins the Washout period) will be included in the single-blind period (i.e., the single-blind period lasts from the day after Visit 4 up to and including Visit 5).

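### The placebo period is meant to show how long the effect lasts, but the SAP reduces it to one average over a period that protocol v7 allows to run from 5 to 23 days

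*SAP*

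**What the plan says.** - **Purpose.** Protocol 4.4: "The purpose of the placebo period is to determine the duration of the treatment effect once study medication is discontinued".
- **Planned length.** Protocol synopsis: "all subjects will be given placebo for 2 weeks (single-blind) followed by 4 weeks of wash-out".
- **Visit windows in protocol v7.** The headings of Protocol 4.4 and 4.5 read "Beginning of Placebo Period (Study Day 26)(- 2 days") and "End of placebo period/ beginning of Wash-Out (Study Day 39) (+/- 8 days").
- **Days counted.** SAP 4.6: "the single-blind period lasts from the day after Visit 4 up to and including Visit 5".
- **Form of the summary.** SAP 4.6.1 says a patient's "CSBM weekly rate over a particular period will be derived using the following algorithm": seven times the number of CSBMs divided by the number of days. For the off-drug periods, "all available data in those periods, excluding observations on the date of the single-blind placebo visit as described before, will be used".
- **Analysis windows.** SAP 4.2: "No visit windows will be applied".
- **Later use.** SAP 4.6.5 analyses the period rate by ANCOVA as change from baseline, and repeats this with the fixed-dose value as the reference. The trend test in SAP 4.6.3 enters the single-blind period as one point, coded 2.

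**The concern.** To learn how long an effect lasts, one has to look at it at known times after stopping. Here a subject seen early contributes only the first days off drug, and a subject seen late contributes more than three weeks. If the effect fades, the first looks as if more was retained than the second, even when both lose it at the same speed.

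Nothing else in the plan for bowel rates restores the timing. There is no weekly rate, common window, time-to-loss measure or adjustment for period length. Changing the ANCOVA reference to the fixed-dose value leaves the period average as it is. Washout is a second single average, and it includes days after the original laxatives restart on washout day 22 (Protocol 4.5).

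SAP 4.6.1 does control length elsewhere: baseline uses at most the last 14 diary days, and a short fixed-dose period is extended to seven days. The off-drug periods, where timing is the question, have no such rule. What is at stake is whether the report can say anything sound about duration of effect.

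**Working it through.** **Inputs.** Visit 4 on Day 24 to 26 (Protocol 4.4). Visit 5 on Day 31 to 47 (Protocol 4.5). Period length = Visit 5 day minus Visit 4 day (counting rule in SAP 4.6).

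**1. The stated length.** 39 − 26 = 13 days, or 14 if both visit days are counted. This agrees with the synopsis figure of two weeks.

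**2. The range allowed.**
- Protocol v7: 31 − 26 = 5 to 47 − 24 = 23 days.
- If the ±8 is counted from the actual Visit 4: 13 − 8 = 5 to 13 + 8 = 21 days.
- If the Visit 5 window is +8 only: 39 − 26 = 13 to 47 − 24 = 23 days. Margin comments in the protocol leave open whether a window is +8 or ±8, without naming the visit.
- SAP Table 1 (Visit 5 ±2 days): 37 − 26 = 11 to 41 − 24 = 17 days.
- SAP Figure 1 (Visit 4 on Day 25, −3): 37 − 25 = 12 to 41 − 22 = 19 days.

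**3. Individual subjects.** Assume the effect decays exponentially from Visit 4 with half-life h, and let k = ln 2 / h. The mean share retained over T days is R = (1 − e^(−kT)) / (kT). For h = 5 and T = 5, kT = 0.693 and R = 0.5 / 0.693 = 72%. For h = 5 and T = 23, kT = 3.188 and R = 0.959 / 3.188 = 30%.

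| Half-life | 5 days | 13 days | 23 days | 5-day ÷ 23-day |
|---|---|---|---|---|
| 3 d | 59% | 32% | 19% | 3.2 |
| 5 d | 72% | 46% | 30% | 2.4 |
| 10 d | 85% | 66% | 50% | 1.7 |

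If the shortest period is 13 days, the contrast between 13 and 23 days is 1.3- to 1.7-fold.

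R depends only on T/h. A 4-day half-life seen over 5 days therefore gives the same mean as a half-life of 4 × 23/5 = 18.4 days seen over 23 days (67% in both). The planned summary cannot tell the two apart.

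**4. Group mean.** Give equal weight to all 3 × 17 = 51 combinations of Visit 4 and Visit 5 dates. The mean retained share is 32%, 46% and 65% for half-lives of 3, 5 and 10 days, against 32%, 46% and 66% at 13 days. The SD between subjects due to timing alone is about 10 percentage points. If every Visit 5 falls on Day 39 to 47 instead, the means are 24%, 37% and 57%.

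**5. What fixed windows would show.** The mean from day a to day b is (e^(−ka) − e^(−kb)) / (k(b − a)). Days 1-7 against days 8-14 give 50% and 10% (h = 3), 64% and 24% (h = 5), and 79% and 49% (h = 10). The fade is visible directly and does not depend on when Visit 5 took place.

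**The case against.** A reader might infer that clinic scheduling changes the trial's reported result up to threefold. The documents do not support that. The threefold figure contrasts two subjects at opposite ends of the windows, whereas the endpoint is analysed as a group mean, and step 4 shows that mean barely moves under even scatter. On the planning difference of 3.55 − 1.28 = 2.27 CSBMs per week, 10 points is about 0.23 per week, small beside the planning SD of 3.88. Only a systematic shift of visit dates would move the group mean, and the documents suggest none.

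A reader might also infer bias between ENT-01 and placebo. None is shown. The windows are the same in both arms, and subjects are not told that the Visit 4 supply is placebo. Timing driven by symptoms could differ by arm, but that is speculation.

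Nor does the exploratory objective fail as written. It asks about a change (synopsis) or decrease (Protocol 3.3, SAP 1.2.3) in efficacy in these periods, and a period mean answers that. Duration appears as the stated purpose in the visit narrative of Protocol 4.4 and 4.5.

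The v7 windows were widened in Amendment 7, so the 5-to-23-day range applies only to subjects seen under v7 and not to the 72 subjects of the first part.

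All of this stands and limits the size of the point. What remains is that one mean of variable length cannot answer the duration question that the protocol sets for this period.

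**Conclusion.** The point holds as a matter of interpretation on an exploratory endpoint. The 5-to-23-day range and the single average follow from the current text. The 1.7- to 3.2-fold contrast concerns individual subjects at the extremes and rests on an assumed exponential decay with a half-life of 3 to 10 days. If the effect does not fade, period length affects only precision. With evenly scattered visits the group mean stays near its 13-day value. If all Visit 5 dates fell on Day 39 to 47, it would drop to about 24%, 37% and 57%. Even if the Visit 5 window is +8 only, the mean still cannot show when the effect is lost. Primary and secondary endpoints are unaffected.

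**What to change.** In SAP 4.6.1 and 4.6.5:

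- Add CSBM and SBM rates for days 1-7 and days 8-14 after the Visit 4 date, whatever the Visit 5 date, with the same rate formula and ANCOVA.
- Base any statement about duration of effect on these windows, and keep the planned whole-period mean alongside.
- Flag days after Visit 5, when placebo tablets have stopped, and give a sensitivity summary restricted to on-placebo days.
- Say how a subject who leaves before day 14 is handled. The existing rule would count days without diary data as days with no CSBM.

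**Cost.** SAP wording and programming only. Daily diaries continue through washout, and both windows end before laxatives restart on washout day 22, even with the earliest Visit 5. Seven-day rates are noisier than a 13-day rate. The windows also mix conditions for some subjects. Days 8-14 include no-tablet days whenever the placebo period is under 14 days, which is one day for the nominal 13-day subject. With a 5- or 6-day period, part of days 1-7 and all of days 8-14 are affected. The flag and the sensitivity summary make this visible but do not remove it.

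Updating the outdated visit schedule in the SAP is clerical. The rates run on actual visit dates, so the derivation does not change.
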